#### Surgical History

- Extent of Resection
- Time from Surgery (years).

#### Prior Cancer Therapy

- Patients with any Prior Cancer Therapy
- Patients with any Prior Radiation Therapy
  - Number of Prior Radiation Therapies
  - Time Since Last Radiation Therapy (months)
- Patients with any Systemic Anticancer Therapy
  - Number of Prior Systemic Therapies (1 or 2+)
  - Time Since Last Systemic Anticancer Therapy (months)
  - Type of Therapy (Immunotherapy, Chemotherapy, Other)
  - Setting
  - Reason for Discontinuation
  - Best Overall Response

## 5.9 Medical History

Medical History will be presented for the Safety Analysis Set by actual treatment. Medical history will be presented by Medical Dictionary of Regulated Activities (MedDRA) primary system organ class and preferred term.

Separate tabulations of previous and ongoing conditions at Screening will be presented by actual treatment arm and overall, for the Safety Analysis Set. Previous medical history is defined as any medical history with an end date before Screening. Concomitant medical history is defined as any medical history that is reported as ongoing or has an end date on or after the date of Screening. All medical history will be listed.

QMD Ref: Worldwide-TMP-ST-054-1.0 Effective: 12Aug2022	Governing QMD: Worldwide-SOP-ST-026
Confidentiality Statement	

This document is the property of Worldwide Clinical Trials Inc. and may not be duplicated, copied, altered or removed from company without prior approval from Worldwide Quality Assurance or in compliance with Worldwide Standard Operating Procedures.

Worldwide Clinical Trials Controlled Quality Management Document		
 WORLDWIDE CLINICAL TRIALS	Sponsor:	Flamingo Therapeutics
	Protocol Number:	FLM-6774-201
STATISTICAL ANALYSIS PLAN		

## 5.10 Prior and Concomitant Medications

Medications will be presented for the Safety Analysis Set by actual treatment. All prior and concomitant medications taken from 30 days prior to enrollment in the study until 30 days after the patient's last dose of the study treatment will be captured in the CRF. Medication terms will be coded as per the WHO Drug dictionary (version B3 Global Mar-2023) and presented by preferred term and ATC level 2 term.

Separate tabulations will be produced for prior and concomitant medications presented by the actual treatment group and overall, for the Safety Analysis Set. Prior Medication is defined as any medication with an end date prior to the first dose of any study drug. Concomitant Medication is defined as any medication that is reported as ongoing or has an end date on or after the date of first dose of any study drug.

## 5.11 Exposure and Compliance to Study Drug

Danvatirsen is an investigational medicinal product (IMP). Pembrolizumab is the standard of care. Collectively, these 2 drugs are referred to as the “study drug”.

The following exposure to study drug parameters will be summarized for the Safety Analysis Set for both Danvatirsen and Pembrolizumab

- Treatment Cycles Completed
- Treatment Duration (Months)
- Treatment Duration of Any Study Drug (Months)
- Number of Doses
- Number of Cycles Infusion Interrupted
- Number of Doses Delayed
- Number of Doses Skipped
- Dose Reductions (Danvatirsen only)

All study drug exposure data will be listed.

QMD Ref: Worldwide-TMP-ST-054-1.0_Effective: 12Aug2022	Governing QMD: Worldwide-SOP-ST-026
Confidentiality Statement	

This document is the property of Worldwide Clinical Trials Inc. and may not be duplicated, copied, altered or removed from company without prior approval from Worldwide Quality Assurance or in compliance with Worldwide Standard Operating Procedures.

Worldwide Clinical Trials Controlled Quality Management Document			
 WORLDWIDE CLINICAL TRIALS	Sponsor:	Flamingo Therapeutics	
	Protocol Number:	FLM-6774-201	
STATISTICAL ANALYSIS PLAN			

## 5.12 Efficacy Analyses

All efficacy analyses will be presented by planned treatment for the FAS.

All statistical tests will be performed using a two-tailed 5% overall significance level, unless otherwise stated. All comparisons between treatments will be reported with 90% and 95% confidence intervals for the difference.

The following efficacy parameters will be derived as per RECIST v1.1 for the FAS.

- Overall Response Rate
- Disease Control Rate
- Complete Response Rate
- Duration of Response
- Progression-Free Survival
- Overall Survival

A summary of RECIST v1.1 tumor assessments, methods, and criteria are presented in Appendix 5 of the protocol. All efficacy parameters are derived from overall response as per RECIST v1.1. Overall response at each tumor assessment is determined using measurements of both target and non-target lesions. The overall response categories are as follows.

All target lesion, non-target lesion, and new lesion data will be listed separately.

Overall Response Categories by RECIST v.1.1	
CR	Complete Response
PR	Partial Response
SD	Stable Disease
PD	Progressive Disease
NE	Not Evaluable

A response of CR or PR must be confirmed by a repeat assessment at least 4 weeks after the initial CR or PR. A tumor assessment at least 35 days after the first dose is required for an overall response of SD, otherwise the BOR is considered not evaluable (NE).

Overall response rate (ORR), complete response rate (CR), and disease control rate (DCR) are each calculated using the subject's best overall response (BOR) on study. This is determined based on the following hierarchy for overall response category:

CR > PR > SD > PD > NE

Tumor assessments after the first PD will not be considered for BOR.

QMD Ref: Worldwide-TMP-ST-054-1.0_Effective: 12Aug2022	Governing QMD: Worldwide-SOP-ST-026
Confidentiality Statement	

This document is the property of Worldwide Clinical Trials Inc. and may not be duplicated, copied, altered or removed from company without prior approval from Worldwide Quality Assurance or in compliance with Worldwide Standard Operating Procedures.

Worldwide Clinical Trials Controlled Quality Management Document			
 WORLDWIDE CLINICAL TRIALS	Sponsor:	Flamingo Therapeutics	
	Protocol Number:	FLM-6774-201	
STATISTICAL ANALYSIS PLAN			

When a patient has at least one overall response of CR or PR, BOR will be assigned using the following rules. This algorithm is not applied for analyses based on unconfirmed response.

(See [Section 5.12.5](#))

Overall Response	Overall Response of Subsequent Assessment	Best Overall Response (Confirmed)
CR	CR $\geq$ 4 weeks later	CR
CR	PR, SD, or PD	SD if duration criteria* PD otherwise
CR	No Evaluable Assessment	SD if duration criteria* NE otherwise
PR	CR $\geq$ 4 weeks later	PR
PR	PR $\geq$ 4 weeks later	PR
PR	SD	SD
PR	PD	SD if duration criteria* PD otherwise
PR	No Evaluable Assessment	SD if duration criteria* NE otherwise

\* Assessment occurred a minimum of 35 days since Baseline

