- f. To facilitate scheduling of predose assessments, a window of -2 days is allowed to obtain the following procedures prior to dosing a patient: physical examination, weight, laboratory safety tests (hematology, serum chemistry, and coagulation), urinalysis, and thyroid function tests.
- g. Vital signs include temperature, pulse, respiratory rate, blood pressure, and oxygen saturation.
- h. For female patients of childbearing potential, serum or urine. The pregnancy test at the 90 day safety follow up visit is required for all patients in the UK and as clinically indicated for all other patients.
- i. Patients are to be followed up for 30 days (+7 days) after the last dose of study treatment for any new reports of AEs, SAEs, and concomitant medications. Tracking of AEs will continue for all patients treated with pembrolizumab for 90 days (±7 days) after the last dose of pembrolizumab or until the initiation of subsequent anticancer therapy.

Flamingo Therapeutics
Activity and Safety of Danvatirsen and Pembrolizumab in HNSCC
8 May 2025

Trial ID: FLM-6774-201
Amendment 4

- j. Tumor assessments performed within 30 days of C1D1 may be used as the baseline tumor assessments. Tumor assessments will be performed every 6 weeks until tumor progression. Patients who discontinue treatment for reasons other than PD will continue to undergo tumor assessments every 6 weeks until PD or the initiation of new anticancer therapy. To facilitate scheduling of tumor assessments, a window of ± 7 days is allowed.
- k. For C1 Week 1, danvatirsen will be administered on D1, D3, and D5 as a loading dose period. Starting with C1 Week 2, danvatirsen will be administered every week on D1, D8, and D15 of each treatment cycle; doses will have a ± 2 -day dosing window.
- l. For pembrolizumab, a window of ± 7 days is allowed for dosing days. Patients will receive pembrolizumab Q3W on D1 of each cycle.
- m. For C1 Week 1, intense PK sampling will be performed on D1 and D5 for 10 US patients in the danvatirsen + pembrolizumab arm. Sparse PK sampling also occurs on C2D1, C5D1 and EOT for all patients in the danvatirsen + pembrolizumab arm. Detailed PK sampling times are provided in [Table 7](#).
- n. ADA will be assessed for danvatirsen + pembrolizumab patients at C1D1, C2D1, C5D1, and EOT, as shown in [Table 8](#).

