9.7 Analysis of Efficacy

The primary efficacy analysis for ORR, as well as the interim analysis for PFS and OS, will be conducted once all patients are treated and followed for a minimum of 3 months (2 radiologic scans). The final analysis for PFS and OS will be conducted after all patients have been followed for a minimum of 15 months, unless the study is deemed futile at the interim or primary analysis stage.

The overall response will be assessed by the Investigator based on the RECIST v1.1 criteria at each timepoint specified the SoA ([Section 8.1](#)). The best overall response (BOR) will be assessed from response assessments occurring after the first dose of either study treatment up to the first documented assessment of PD that is prior to the initiation of a new anticancer therapy. Objective response (i.e., BOR of PR or CR) will require confirmation of the response (CR or PR) at least 4 weeks after the initial CR or PR.

The ORR will be defined as the proportion of patients with a confirmed objective response as assessed by the Investigator in the FAS. Patients who receive at least one dose of either study treatment but have no valid postbaseline radiographic assessment will be considered non-responders. The ORR will be reported along with the corresponding 2-sided 90% and 95% Clopper-Pearson exact CI. The criteria for promising ORR at the primary analysis are detailed in [Table 9](#) and, in addition, a comparison between the 2 treatment groups will be performed based on Fisher's exact test.

DOR is defined as the date of the patient's first confirmed BOR of CR or PR to the earliest date of documented progression or death if no prior evidence of disease progression, for all patients in the FAS with a confirmed objective response. A patient that starts a new anticancer therapy prior to disease progression will be censored at the date of last valid disease assessment prior to the start of the new anticancer therapy. All other patients without progression or death will be censored at the date of the last valid disease assessment. DOR will be summarized using Kaplan-Meier methods.

The DCR, which includes a BOR of CR, PR, or SD, will be analyzed similar to ORR.

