Target Lesions. When more than one measurable tumor lesion is present at baseline all lesions up to a maximum of 5 lesions total (and a maximum of 2 lesions per organ) representative of all involved organs should be identified as target lesions and will be recorded and measured at baseline. Target lesions should be selected on the basis of their size (lesions with the longest diameter), be representative of all involved organs, but in addition should be those that lend themselves to reproducible repeated measurements. Note that pathological nodes must meet the criterion of a short axis of ≥ 15 mm by CT scan and only the short axis of these nodes will contribute to the baseline sum. All other pathological nodes (those with short axis ≥ 10 mm but < 15 mm) should be considered non-target lesions. Nodes that have a short axis < 10 mm are considered non-pathological and should not be recorded or followed. At baseline, the sum of the target lesions (longest diameter of tumor lesions plus short axis of lymph nodes: overall maximum of 5) is to be recorded. After baseline, a value should be provided on the case report form for all identified target lesions for each assessment, even if very small. If extremely small and faint lesions cannot be accurately measured but are deemed to be present, a default value of 5 mm may be used. If lesions are too small to measure and indeed are believed to be absent, a default value of 0 mm may be used.

Non-Target Lesions. All non-measurable lesions (or sites of disease) plus any measurable lesions over and above those listed as target lesions are considered *non-target lesions*. Measurements are not required but these lesions should be noted at baseline and should be followed as “present” or “absent.”

Response.

All patients will have their BEST OBJECTIVE RESPONSE from the start of study treatment until the end of treatment classified as outlined below:

Complete Response (CR): disappearance of target and non-target lesions and normalization of tumor markers. Pathological lymph nodes must have short axis

measures <10 mm (note: continue to record the measurement even if <10 mm and considered CR). Residual lesions (other than nodes <10 mm) thought to be non-malignant should be further investigated by cytology specialized imaging or other techniques as appropriate for individual cases before CR can be accepted. Confirmation of response is required and should occur no less than 4 weeks after the initial response.

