### 5.12.2 Primary Efficacy Analysis

The primary efficacy analysis for ORR will be conducted once all patients are treated and followed for a minimum of 3 months (2 radiologic scans).

The number and percentage of patients with each BOR category will be summarized.

The ORR will be defined as the proportion of patients with a confirmed objective response as assessed by the Investigator in the FAS. “Patients who receive at least one dose of either study

QMD Ref: Worldwide-TMP-ST-054-1.0_Effective: 12Aug2022	Governing QMD: Worldwide-SOP-ST-026
Confidentiality Statement	

This document is the property of Worldwide Clinical Trials Inc. and may not be duplicated, copied, altered or removed from company without prior approval from Worldwide Quality Assurance or in compliance with Worldwide Standard Operating Procedures.

Worldwide Clinical Trials Controlled Quality Management Document			
 WORLDWIDE CLINICAL TRIALS	Sponsor:	Flamingo Therapeutics	
	Protocol Number:	FLM-6774-201	
STATISTICAL ANALYSIS PLAN			

treatment but have no valid post-baseline tumor assessment or not available confirmed BOR will be considered non-responders.”

The ORR estimate along with the corresponding 2-sided 90% and 95% confidence interval using Clopper-Pearson exact binomial test will be presented for each treatment arm.

Comparison of the ORR between treatment arms will be analyzed using Fisher’s Exact test and by reporting the risk difference and corresponding 90% and 95% confidence intervals. Both a 1-tailed and 2-tailed p-value for Fisher’s Exact test will be provided. The risk difference for ORR is calculated as the difference in ORR between both treatment arms. Confidence intervals for the risk difference will be calculated using the Wald Method.

The following SAS code will be used, where adrs\_freq is a frequency table of planned treatment by responder status. (Sorted so that first row is responders for the combination arm).

ORR Estimate and Corresponding Exact Binomial Confidence Intervals:

```
ods output binomial=<outdata>;
proc freq data=adrs_freq;
  tables avalc / binomial(level="RESPONDER") alpha=0.05;
  by trt01pn;
  weight count;
run;
Lower Limit is nvalue1 where name1="XL_BIN".
Upper Limit is nvalue1 where name1="XU_BIN".
Use alpha=0.10 for 90% CI.
```

Risk Difference and Corresponding Confidence Intervals:

```
ods output riskdiffcol2=<outdata>;
proc freq data=adrs_freq order=data;
  tables trt01pn*avalc / riskdiff alpha=0.05;
  weight count;
run;

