#### 5.12.4.2 Duration of Response

Duration of response (DOR) is defined as the date of the patient's first BOR of CR or PR to the earliest date of documented progression or to death if no prior evidence of disease progression. DOR will be calculated as follows for all patients in the FAS population with a confirmed objective response. The date of the first confirmed response is based on the first instance of CR or PR that is confirmed by repeat assessments at least 4 weeks later.

QMD Ref: Worldwide-TMP-ST-054-1.0_Effective: 12Aug2022	Governing QMD: Worldwide-SOP-ST-026
Confidentiality Statement	
This document is the property of Worldwide Clinical Trials Inc. and may not be duplicated, copied, altered or removed from company without prior approval from Worldwide Quality Assurance or in compliance with Worldwide Standard Operating Procedures.	

Worldwide Clinical Trials Controlled Quality Management Document			
 WORLDWIDE CLINICAL TRIALS	Sponsor:	Flamingo Therapeutics	
	Protocol Number:	FLM-6774-201	
STATISTICAL ANALYSIS PLAN			

$$DOR \text{ (Months)} = \frac{(Date \text{ of } PD, \text{Death, or censoring} - Date \text{ of } 1^{\text{st}} \text{ confirmed CR or PR}) + 1}{30.4375}$$

DOR may be censored to a stop date other than PD or death, as described in the censoring rule table of [Section 5.12.4.5](#).

Kaplan-Meier estimates of 25th, 50th and 75th percentiles for DOR will be presented. Corresponding 95% confidence intervals using Greenwood's formula will be provided. Minimum and Maximum DOR will be presented.

The following SAS code will be used.

```
proc lifetest data=adtte timelist=3 6 9 12 reduceout outsurv=<outdata>;
  time aval*cnsr(1);
  by trt01pn;
run;
```

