#### 5.12.4.5 Censoring Rules for Time-to-Event Parameters

Progression-Free Survival and Duration of Response Censoring			
#	Event Description	Stop Date Used	Outcome
1	Documented radiological PD before initiation of non-study anti-cancer treatment	Date of the first tumor assessment that determined PD	Event
2	Death during the study with no prior PD and no prior initiation of non-study anti-cancer treatment	Date of death	Event
3	Radiographic PD or death after a missed (or not available / not evaluable) tumor response assessment**	Date of last adequate tumor assessment prior to missed tumor assessment	Censored
4	Patient administered new anticancer therapy prior to disease progression	Date of last valid disease assessment prior to start of new anticancer therapy	Censored
5*	No evaluable post-Baseline tumor assessment	Date of first dose	Censored
6*	Patient without documented progression or death	Date of the last valid disease assessment date	Censored
7*	Patient withdrawal or lost to follow-up	Date of the last valid disease assessment	Censored
Overall Survival Censoring			
#	Event Description	Stop Date Used	Outcome
1	Death from any cause	Date of death	Event
2	Patient withdrawal or lost to follow-up	Date of the last contact	Censored
3	Patient without documentation of death as of the data cutoff	Date of last contact where subject known to be alive.	Censored

\*Not applicable to Duration of Response

\*\*A tumor response assessment is considered missed if more than 13 weeks (91 days) has elapsed since the last image-based tumor response assessment. If a subject develops progressive disease or dies directly after this interval, the tumor response assessment will be excluded from analysis and censored to the last evaluable assessment. However, if a response assigned as CR, PR, or SD is obtained after more than 13 weeks, then the tumor response will not be excluded.

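### SAP 5.12 closes the best-response window only at first progression, with no cut-off at new anticancer therapy, so a recorded scan on non-study treatment could enter the primary ORR

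*SAP*

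**What the plan says.** The primary endpoint in SAP 5.12.2 is the "proportion of patients with a confirmed objective response as assessed by the Investigator in the FAS". It is built from BOR, which SAP 5.12 takes over the patient's time on study, with one stated limit: "Tumor assessments after the first PD will not be considered for BOR". The table of confirmation rules in the same section requires a gap of at least 4 weeks. It says nothing about treatment received in that gap.

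Three other places set a different limit:

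- Protocol 9.7 collects response assessments after first dose "up to the first documented assessment of PD that is prior to the initiation of a new anticancer therapy".
- Protocol Appendix 5, to which SAP 5.12 refers for RECIST methods and criteria, defines "BEST OBJECTIVE RESPONSE from the start of study treatment until the end of treatment".
- SAP 5.12.4.5, row 4, covers PFS and DOR when new therapy starts before progression. The stop date is the "Date of last valid disease assessment prior to start of new anticancer therapy", and the patient is censored. The footnote that exempts DOR applies to rows 5 to 7 only, so row 4 governs DOR.

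The DOR start date in SAP 5.12.4.2 is "based on the first instance of CR or PR that is confirmed by repeat assessments at least 4 weeks later", with no reference to new therapy. SAP section 9 declares one change from the protocol, the earlier final analysis after early termination, and nothing about the BOR window.

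**The concern.** The primary endpoint should measure response to the randomised treatment. Under the SAP rule, a patient without PD who starts other anticancer treatment stays inside the BOR window, so a later scan can supply a first response or the confirmation of one. The SAP foresees new therapy before PD for PFS and DOR, but not for the endpoint on which the decision rests. ORR and DOR can then disagree about the same patient. DCR and complete response rate use the same BOR. The unconfirmed-response analysis in SAP 5.12.5 is more exposed, because one scan is enough.

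The trial is open-label with investigator-assessed response, so the plan gives no assurance that such cases would be equally frequent in the two arms.

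**Working it through.** **1. One patient, four rules.** Take a patient with no PD who starts non-study therapy and then has a scan showing PR.

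| Rule | Is the later scan used? |
|---|---|
| SAP 5.12 (BOR) | Yes; only PD closes the window |
| Protocol 9.7 (BOR) | No on the natural reading. Read literally, the new-therapy phrase qualifies the PD, so no end date applies to this patient |
| Protocol Appendix 5 (BOR) | No, if study treatment has ended |
| SAP 5.12.4.5 row 4 (DOR) | No; DOR stops at the last scan before the new therapy |

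**2. Can such a scan be on file?** Scheduled imaging stops at new therapy (Protocol 3.1, 7.6.3, 7.7), and Protocol 7.4 then moves the patient to survival follow-up. The remaining routes are:

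- Imaging at the investigator's discretion (Protocol 7.7).
- An end-of-treatment scan done late, after new therapy has begun.
- Prohibited therapy given while scans continue. Note j in Protocol 8.1 says "Tumor assessments will be performed every 6 weeks until tumor progression"; its new-therapy stop, in the next sentence, covers only patients who have discontinued treatment.

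The documents give no frequency for any of these.

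**3. DOR.** Formula (SAP 5.12.4.2): (stop date − first confirmed CR/PR + 1)/30.4375 months. All days below are assumed.

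- First response and confirmation both after new therapy, last earlier scan on day 84, first PR on day 126: (84 − 126 + 1)/30.4375 = −1.35 months.
- Last earlier scan on day 42, first PR on day 63, 84 or 126: −20/30.4375 = −0.66, −41/30.4375 = −1.35, −83/30.4375 = −2.73 months.
- PR first seen before new therapy and confirmed only afterwards: the censoring date is on or after the first PR, so DOR is at least 1/30.4375 = 0.03 months. The patient counts in ORR, but DOR is not negative.

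**4. The plan's own design figures.** Inputs (Protocol 9.2): Beta(0.5, 0.5) priors, λ = 0.96, α = 0.94, interim 13/26, final 27/54 (control/combination). The interim cut-off is 0.96 × (39/81)^0.94 = 0.483. The rebuilt boundaries match every row of Table 9. Exact enumeration gives:

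| Figure | Recomputed | Table 10 |
|---|---|---|
| Power at 15% v 43% | 82.6% | 82.7% |
| Type I error at 15% v 15% | 4.5% | 4.6% |
| Early stopping at 15% v 15% | 46.4% | 46.1% |
| Early stopping at 15% v 43% | 1.9% | 1.9% |

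These figures do not depend on where the BOR window ends, so adding the cut-off leaves them unchanged.

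**5. Weight of one patient at the planned size.** One responder moves ORR by 1/27 = 3.7 points in control or 1/54 = 1.9 points in combination. In Table 9, 4 control responders require a difference above 13, so 4 + 14 = 18 combination responders; 5 require a difference above 15, so 5 + 16 = 21.

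| Combination | Control | Posterior Pr(superior) | Above 0.96? |
|---|---|---|---|
| 17/54 | 4/27 | 0.950 | No |
| 18/54 | 4/27 | 0.965 | Yes |
| 18/54 | 5/27 | 0.921 | No |

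**6. Assumed range.** Let a share m of non-responders be wrongly counted, so that the observed ORR is p + (1 − p)m. With m from 2% to 5%:

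- Both arms: power 79.9% to 76.1%, type I error about 4.4%.
- Control only: observed control ORR 0.167 to 0.1925, power 77.0% to 67.6%.
- Combination only: type I error 6.5% to 10.4%.

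For scale, in control at p = 0.15 this is 27 × 0.85 × 0.02 = 0.5 to 27 × 0.85 × 0.05 = 1.1 patients. Nothing in the documents says that m reaches these values.

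**The case against.** The strongest reply is that the protocol already prevents the problem. Imaging stops at new therapy in several places. Concurrent anticancer treatment and palliative radiotherapy are prohibited (Protocol 5.5.3, 5.6). A major deviation is a ground for discontinuation (Protocol 6.1). The end-of-treatment visit is due promptly once both drugs stop, and imaging from the previous 30 days is not repeated (Protocol 7.6; 8.1, note a). The SAP also refers to Appendix 5, whose window ends with treatment. Most of this stands, and it makes the exposure narrow. It does not close the gap: visit rules decide which scans are scheduled, whereas the BOR rule decides which recorded scans the program uses, and discretionary imaging is expressly allowed.

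A reader might infer that the SAP removed a clear protocol cut-off. The documents do not support that. Protocol 9.7 is itself loosely worded and, taken literally, sets no end date for a patient who starts new therapy before any PD.

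The illustration at 18/54 can also fairly be called a chosen margin. It is. The go/no-go criteria are non-binding (Protocol 9.2, 9.10.2), and because of early termination the final analysis may not have 54 and 27 patients.

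**Conclusion.** The omission is certain: SAP 5.12 has no new-therapy cut-off for BOR, it does not agree with Protocol 9.7, Appendix 5 or its own DOR rule, and the difference is undeclared. The consequence is conditional: a response on non-study treatment could count, or be confirmed, in the primary ORR if such a scan is recorded.

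Two stronger inferences should be resisted. One is that responses to non-study treatment routinely enter the ORR; they need a scan outside the intended schedule or a breach of the prohibited-therapy rule. The other is that negative DOR is a general result; it needs both the first response and its confirmation, at least 4 weeks apart, to fall after new therapy without intervening PD.

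The number of patients affected and any imbalance between arms are unknown. The shift from 0.965 to 0.921 assumes the full 54 v 27 and a result at the decision boundary. Severity: should-fix, not must-fix.

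**What to change.** In SAP 5.12, replace the sentence on assessments after first PD with:

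> Only tumor assessments from first dose up to the earlier of first PD and the start of new anticancer therapy are considered for BOR, and the confirmatory assessment must also fall within this window.

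Use the same definition and date of new anticancer therapy as row 4 of SAP 5.12.4.5. If radiotherapy to a lesion, or its resection, is meant to count, define it identically in both places; otherwise ORR and DOR could again use different triggers. Apply the window to DCR, complete response rate and the unconfirmed-response analysis as well. Align the wording of Protocol 9.7 and Appendix 5. If the protocol is not amended, record the rule in SAP section 9.

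The SAP cost is one sentence and one date condition in the BOR program. Initiation of new therapy is already collected (Protocol 7.6.3). With the cut-off in place, the first response cannot fall after the row 4 censoring date, so DOR under that row is at least one day. The downside is that ORR may be slightly lower.
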